### **6.4 6 Weeks (Day 28-56)**

All subjects will undergo a model-based RSA examination. For all sites, the 6-week exam will be used as the reference examination. RSA radiographs will be obtained with subjects in a supine position. A duplicate RSA exam will be conducted at this time-point to calculate the intra-subject measurement error.

Additionally, the subject will have the following health and functional status evaluations:

- Harris Hip Score; ROM optional
- Hip Evaluation
- HOOS Jr.
- Forgotten Joint Score
- Adverse Events (if applicable)
- Radiographs
  - AP Femur
  - Lateral

The information collected from the '6 Week' visit will be populated on the appropriate eCRFs as indicated in the Time and Events Table (Section 1.1).

NOTE: Any subject that is unable to complete their 6 week visit due to the COVID-19 Pandemic can be replaced; as many endpoints use this timepoint as the baseline value. Subjects unable to complete their 6 week visit will not be withdrawn because of this missing visit but continue to be followed according to the protocol.

## 6.5 3 Month, 6 Month, 1 Year and 2 Year Visits

The subject will have the following health and functional status evaluations:

- Harris Hip Score
- Hip Evaluation
- HOOS Jr.
- Forgotten Joint Score
- Adverse Events (if applicable)
- Radiographs
  - AP Femur
  - Lateral
- RSA Exam (supine position)

The information collected from these visits will be populated on the appropriate eCRFs as indicated in the Time and Events Table (Section 1.1).

## 6.6 Unscheduled Visit

If a subject requires an additional visit during a study interval for their study hip, and is seen by one or more person listed on the Delegation of Authority Log, then the following information shall be repeated:

- Harris Hip Score
- Hip Evaluation
- HOOS Jr.
- Forgotten Joint Score
- Adverse Events (if applicable)

If a subject has an unscheduled visit after the 6 week interval (outside defined protocol window) for their study hip, with one or more person listed on the Delegation of Authority Log then the following information shall be collected:

- Harris Hip Score
- Hip Evaluation
- HOOS Jr.
- Forgotten Joint Score
- Adverse Events (if applicable)
- Radiographs
  - AP Femur
  - Lateral
- RSA Exam (supine position) if RSA Exam was not conducted in-window for previous visit.  
If subject is seen multiple times outside of the same defined protocol window, only one RSA Exam is required.

## 6.7 Radiostereometric Analysis (RSA)

The RSA analysis will be the responsibility of the Canadian RSA Network. In summary, model based RSA software (RSAcore, Leiden, Netherlands) will be used for analysis, employing computer-models of the DePuy Synthes implants and inserted beads representing the bone rigid body. A central analysis service will be employed to analyze anonymized radiographs in a standard manner. DePuy Synthes will provide production CAD models as required for this analysis.

Three-dimensional migration measurements will be made of the acetabular shell relative to the bone beads. The 6-week examination will be used as reference against which the 3-month, 6-month, 1-year and 2-year post-operative exams will be compared. Results obtained from the model based RSA software will be changes from the 6-week (baseline) examination and will report the following at 3 months, 6 months, 1 year and 2 years:

- X, Y and Z translation measurements in mm from baseline;
- X, Y and Z rotation measurements in degrees from baseline;
- Maximal total point motion (one measurement in mm of maximal migration).

Three-dimensional migration of the Pinnacle Acetabular Shell shall be determined from the software.

Linear head penetration (in mm) will be performed by examining the change in distance between the center of the femoral head and the center of the acetabular shell between the 6-week (baseline) exam and 1 year and 2 year exam. The femoral head center is determined by fitting a CAD sphere to the articular region of the femoral head (ignoring the trunnion area). The acetabular shell center is determined in a similar manner but also uses the silhouette of the cup face to determine its' centerpoint.

## 7 ADVERSE EVENT REPORTING

### 7.1 Adverse Events

An Adverse Event is any untoward medical occurrence in a subject, regardless if there is a relationship between the adverse event(s) and the study device(s).

At each evaluation of the subject enrolled in a clinical investigation, the Investigator determines whether any adverse events (AE) have occurred and determines their relationship to the study devices or procedure. For the purposes of this study, only serious adverse events (see Section 7.2), device and/or procedure related adverse events will be reported to the Sponsor.

All reportable adverse events, study device malfunctions and other product issues must be recorded in the medical records and entered into electronic Case Report Forms (eCRFs) within two weeks of awareness the AE occurred. Upon entry of an AE into the eCRF, designated members of the DePuy Synthes clinical team will receive an email alert describing the AE.

## 7.2 Serious Adverse Events

**Serious Adverse Events (SAEs)** are defined as any adverse event that:

1. Led to a death,
2. Led to a serious deterioration in the health of the subject that,
  - a. Resulted in life-threatening illness or injury,
  - b. Resulted in permanent impairment of a body structure or a body function,
  - c. Required in-patient hospitalization or prolongation of existing hospitalization
  - d. resulted in medical or surgical intervention to prevent life threatening illness or injury or permanent impairment to a body structure or a body function,
3. Led to fetal distress, fetal death or a congenital abnormality or birth defect

A planned hospitalization and/or medical intervention for pre-existing conditions documented in the study records that have not changed in severity, or a procedure required by the protocol, without serious deterioration in health, is not considered to be a serious adverse event.

Investigator must submit to DePuy Synthes any SAEs occurring during the study as soon as possible, but within 72 hours, after becoming aware of the event and provide additional information if required by DePuy Synthes. All SAEs need to be followed until the event is resolved (with or without sequelae), additional information is located in Section 7.3. The Study Safety Lead of this study will decide if more follow-up information is needed (via electronic queries) in case the event is not resolved at study completion.

The Investigator notifies his/her REB of all SAEs as required by REB policy (and any additional information as required by REB). All SAEs are to be reported to the Sponsor.

## 7.3 Duration of Follow-up After Adverse Events

The Investigator should ensure that adequate medical care is provided to any subject for any adverse events related to the study.

Only SAE, device and/or procedure related Adverse Events will be collected for the purposes of this study. All device or procedure adverse events should be followed until the condition has resolved, or in the case of permanent impairment until the condition stabilizes and clinical outcome has been ascertained, or the study has been completed.

## 7.4 Reporting an Adverse Event

Adverse events are reported from the time of surgery until the subject's study participation has ended (i.e. completion of study or withdrawal of consent). All reported AEs must be followed until the AE has resolved, stabilized, or the study has been completed. Any medical event, that if it had occurred post-operatively would be considered a Serious adverse event, that occurs prior to surgery is to be reported as history on the Medical History eCRF.

The Investigator will record the nature, severity, treatment and outcome of the AE, and will determine its relationship to the investigational products or any protocol mandated procedures involved in the clinical study.

The determination whether the AE is related to the device and/or procedure will be based upon whether a causal relationship between the device and/or procedure and the AE is at least a

reasonable possibility, i.e. the relationship cannot be ruled out. A causal relationship cannot be ruled out if, in the medical judgment of the Investigator, the effect follows a reasonable temporal association with the use of the device and/or is confirmed by the improvement of the effect upon discontinuation of the clinical use of the device, and/or the effect is not reasonably explained by the Subject's clinical state.

Relationship to study device or procedure should be rated as follows:

- 1) Not related (definitely not related): there is no relationship between study device and/or procedure and the event.
- 2) Possibly related (remote possibility, possibly, or probably related): the relationship between study device and/or procedure could exist if there is no contradicting evidence that can reasonably explain the Subject's condition.
- 3) Definitely related (definitely related): the relationship between study device and/or procedure and event does exist and is confirmed upon further investigation by the Investigator.

**The following categories of adverse event severity are to be used:**

Mild	Awareness of sign or symptom that does not interfere with the subject's usual activity or is transient, resolved without treatment and with no sequelae,
Moderate	Interferes, but does not hinder, the subject's usual activity and may require treatment,
Severe	Symptom(s) causing severe discomfort and significant impact on the subject's usual activity and requires treatment or intervention.

Adverse events will be reported by the Investigator to DePuy Synthes via the Adverse Events eCRF.

NOTE: Please refer to Appendix B (Anticipated Adverse Events) where a listing of common surgical adverse events is listed. These adverse events are anticipated and assuming the events are consistent with the normal postoperative course, then they do not have to be reported as adverse events.

## **8    EARLY DISCONTINUATION**

### **8.1    Reasons for Early Discontinuation**

Possible reasons for early discontinuation may include, but are not limited to the following:

- Withdrawal of consent: Subject decides to withdraw from the study. This decision must be an “independent decision” that is documented in the patient study files;
- Adverse event: Adverse event or serious adverse event may not lead to subject discontinuation from the study. If the Investigator decides to discontinue further study related procedures, the subject must still be followed until the adverse event resolves or until a stable clinical endpoint is reached, or the subject withdraws consent (i.e. the subject will continue to be followed for safety);
- If the surgeon deems that screw fixation or any component other than those listed in the protocol is required for that subject;
- Revision of any component;
- Death, and/or
- Early study termination: DePuy Synthes can decide to discontinue the study prematurely for various reasons.

### **8.2    Subject Early Discontinuation**

Every subject should be encouraged to remain in the study until they have completed the protocol-required 2-year follow-up period. If the subject discontinues prematurely from the study, the reason for discontinuation must be documented in the source documents and site files and submitted via eCRF.

Data which have been received on subjects who discontinue prematurely will be included in the analysis of results. Subjects who discontinue prematurely, excluding those withdrawn pre-operatively, intra-operatively or those subjects who were unable to complete their 6 week visit due to the COVID-19 Pandemic, will not be replaced.

### **8.3    Study Early Discontinuation**

DePuy Synthes reserves the right to temporarily suspend or prematurely discontinue this study either at a single site, multiple sites, or at all sites at any time for reasons including, but not limited to, safety or ethical issues, inaccurate or incomplete data recording, non-compliance, or unsatisfactory enrollment with respect to quality or quantity.

If the study is prematurely terminated or suspended, DePuy Synthes or its representatives will inform the Investigators/institutions of the termination or suspension and the reason(s) for the termination or suspension, in accordance with applicable regulatory requirement(s). The REB should also be informed and provided with reason(s) for the termination or suspension by DePuy Synthes or by the Investigator/institution, as specified by the applicable regulatory requirement(s). In addition, arrangements will be made for the return of all study material in accordance with Sponsor procedure for the study.

## 9 STATISTICAL METHODOLOGY

The following sections provide a general description of the statistical plan for the analysis of study data. A separate Statistical Analysis Plan (SAP) document that provides greater detail on data derivations and the analyses to be performed will be finalized prior to database lock. The SAP will reflect the protocol and any amendments that have been implemented at the time the SAP is finalized. Any deviations from the final SAP will be noted in the final clinical summary report.

### 9.1 Study Design

This is a prospective, multi-center, non-randomized, non-controlled study designed to establish the 2-year migration profile of the Pinnacle Acetabular Shell when implanted using 3 different surgical approaches: posterior, anterior, and lateral.

### 9.2 Treatment Assignment

Subjects enrolled will undergo THA using the study devices listed in Section 3.5 and one of the surgical approaches under study: posterior, anterior, and lateral. Centers will be selected for their expertise in one or more of the surgical approaches. Each surgeon will perform the approach they are most comfortable with and have the greatest expertise. In general, subjects enrolled at the Winnipeg site will undergo a posterior approach or direct lateral approach. Subjects enrolled at the London site will undergo a direct anterior approach, direct lateral approach or posterior approach. Enrollment will be closely monitored to ensure a minimum of 30 subjects are enrolled in each surgical approach group. Once a group has reached 30 implantations, Investigators of that approach group will be informed to halt enrollment of further subjects.

### 9.3 Randomization and Blinding Procedures

Not applicable.

### 9.4 Interval Windows

Data collected throughout the study will be assessed for compliance with the protocol-specified visit schedule. **Error! Reference source not found.** Six windows are defined based on the number of days prior to or after surgery, Day 0. Visits conducted within the intervals shown in Table 9-1 will be assessed for compliance with the protocol. If multiple visits fall into the pre-operative window, or into the 6 Week post-operative window, the result collected most proximate to surgery will be utilized. If multiple measurements fall into the 3 Month, 6 Month, 1 Year, or 2 Year window, the last value (furthest from surgery) will be utilized for the analysis. All safety data will be included in the Safety analysis.

Table 9-1 Study Visit Interval Windows per Time and Events Table

Study Visit	Study Interval Window (days)
Pre-Op	-90 to DOS*
Operative	0
Prior to Discharge	Day 1 to Discharge
6 Weeks	28 to 56
3 Months	60 to 120

6 Months	135 to 225
1 Year	275 to 455
2 Years	640 to 820

\* For radiographs Pre-Op study film window is from -270 days to DOS.

## 9.5 Analysis Sets

### Safety Analysis Set

The Safety Analysis Set consists of all enrolled subjects who receive THA surgery. Subjects will be analyzed according to the surgical approach applied during of the study.

### Per Protocol (PP) Analysis Set

The Per Protocol (PP) Analysis Set will be a subset of Safety Set subjects who have no major inclusion/exclusion protocol violations, and who have a baseline RSA exam and at least one post-baseline RSA exam. Subjects will be analyzed according to the actual treatment (surgical approach) received during of the study.

## 9.6 Primary and Secondary Endpoints and Associated Hypotheses

There are no hypotheses associated with the primary or secondary endpoints; endpoints appear below.

### 9.6.1 Primary Endpoint

The primary endpoint is the RSA measured mean superior cup migration (Y translation subsidence in mm) at 2 years.

### 9.6.2 Secondary Endpoints

The secondary endpoints are the following:

- RSA measured subsidence (superior cup migration) at 3 months, 6 months and 1 year.
- Other RSA measurements (X and Z translations in mm, X, Y, and Z rotations in degrees, and maximal total point motion in mm) at all time points
- Linear head penetration at, 1 year and 2 years;
- Harris Hip Score at 6 weeks, 3 months, 6 months, 1 year and 2 years;
- HOOS Jr. at 6 weeks, 3 months, 6 months, 1 year and 2 years;
- Forgotten Joint Score (FJS-12) at 6 weeks, 3 months, 6 months, 1 year and 2 years.

### 9.6.3 Exploratory Endpoints

The following will be summarized as exploratory analyses:

- Correlation of functional and health status outcomes (Harris Hip Score, HOOS Jr, and FJS-12) vs. RSA observations may be explored.

## **9.7 Levels of Significance**

There are no specific hypotheses being tested in this study. To facilitate clinical interpretation, confidence intervals will accompany primary and secondary endpoint estimates and will be 2-sided 95% confidence intervals; these confidence intervals are considered to be exploratory.

## **9.8 Sample Size Justification**

This study sample size was established to provide adequate precision on the mean subsidence estimate at 2 years for each surgical approach. A common standard deviation of 0.2 mm is anticipated. Based upon this standard deviation and a sample size of N=30, a 2-sided 95% confidence interval for each respective surgical approach is anticipated to have a margin of error equal to approximately  $2SE = 2 \times \frac{SD}{\sqrt{n}} = 2 \times \frac{0.2}{\sqrt{30}} = 0.073$  mm. This margin of error was deemed to be an adequate level of precision by the Sponsor.

## **9.9 General Conventions**

All statistical analysis will be performed using SAS® Version 9.3 or higher, unless otherwise noted. A separate Statistical Analysis Plan (SAP) will provide detail on data derivations and the analyses to be performed for the final study report. It will be approved prior to database lock.

Descriptive statistics for continuous variables will include the number of subjects with an observation, mean, standard deviation (SD), median, minimum, and maximum. Descriptive statistics for dichotomous/categorical variables will include the count and percentage of subjects in each category.

Unless specifically stated otherwise, all endpoints will be analyzed by surgical approach and overall, pooling all surgical approaches.

## **9.10 Disposition of Study Subjects**

An overall summary of the number of subjects in each analysis set (Safety and Per Protocol) who had major protocol deviations, who withdrew before study completion, and who completed the study will be tabulated for all surgical approaches combined.

A patient accounting table to present the number of subjects in the Safety Analysis Set at each visit interval will be summarized: theoretical due, deaths, withdrawn, and expected due in the interval.

## **9.11 Demographic and Baseline Characteristics**

Descriptive statistics summarizing demographics and baseline characteristics will be displayed for both the Safety Analysis Set and the Per Protocol Analysis Set. These summaries will include, but are not limited to, age, gender, BMI, general medical conditions, Harris Hip Score, Hoos Jr. and Forgotten Joint Score.

## **9.12 Primary, Secondary, and Safety Endpoint Analyses**

### **9.12.1 Primary Endpoint Analysis**

#### RSA Measured Subsidence at 2 years

The primary endpoint of RSA measured subsidence (Y translation, also known as superior cup migration) results in the 2-year visit window will be summarized on the subset of subjects in the Per Protocol Analysis Set (primary analysis) who have 6 week and 2 year data for the analysis. The analysis will also be conducted on the subset of subjects in the Safety Analysis Set (supportive analysis) who have 6 week and 2 year data for the analysis. Standard continuous summaries will be provided along with 95% confidence intervals. These summaries will be provided for each surgical approach, as well as combined.

### **9.12.2 Secondary Endpoint Analysis**

#### RSA Measured Subsidence at 3 months, 6 months and 1 year

The analysis for this secondary endpoint will be identical to the analyses described for the primary endpoint except conducted on the results in the 3 month, 6 month, and 1 year visit windows, respectively, using the Per Protocol Analysis Set and the Safety Set.

#### Linear Head Penetration at 1 year and 2 years

Linear head penetration will be assessed at 6 weeks, 1 year and 2 years. Results within each visit window will be summarized and changes from baseline will be provided using the Per Protocol Analysis Set.

#### Harris Hip Score at 6 weeks, 3 months, 6 months, 1 year and 2 years

Harris hip scores are assessed at the Pre-Op visit and at 6 weeks, 3 months, 6 months, 1 year and 2 years. Results within each visit window will be summarized and changes from baseline will be provided using the Per Protocol Analysis Set. Standard continuous summaries will be supplemented with 95% confidence intervals. The ROM at 6 weeks is considered optional; the score will be missing for subjects for whom ROM was not performed.

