## 1.1 TIME AND EVENTS SCHEDULE

Event / Visit	Pre-op		Operative	Prior to Discharge	6 Weeks	3 Months	6 Months	1 Year	2 Years
	-270 to DOS	-90 to DOS	Day 0	Day 1 to Discharge	28-56 d	60-120 d	135-225 d	275-455 d	640-820 d
Complete Screening Log		✓							
Obtain Informed Subject Consent		✓							
Verify Inclusion / Exclusion Criteria		✓							
Subject History		✓							
Harris Hip		✓			✓*	✓	✓	✓	✓
Hip Evaluation		✓			✓	✓	✓	✓	✓
HOOS Jr.		✓			✓	✓	✓	✓	✓
Forgotten Joint Score (FJS-12)					✓	✓	✓	✓	✓
Operative Details			✓						
Device Log			✓						
Unscheduled Visit Report ** (Interim Visit)					✓	✓	✓	✓	✓
Adverse Event			✓	✓	✓	✓	✓	✓	✓
End of Study (Withdrawal (W/D)) Form***					If W/D	If W/D	If W/D	If W/D	If W/D
AP View	✓				✓	✓	✓	✓	✓
Lateral View	✓				✓	✓	✓	✓	✓
RSA Exam (supine)					✓ (dbl exam)	✓	✓	✓	✓

\* ROM optional at 6 weeks only

\*\* As Needed

\*\*\* As Applicable

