## **6.11 Handling of Missing Data**

Only subject data which is collected in the study will be utilized in analyses; there will be no imputation of missing data.

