## **8 Appendix A – Questionnaire Scoring**

### **8.1 Harris HIP Score**

The Harris Hip Score was developed for the assessment of the results of hip surgery, and is intended to evaluate various hip disabilities and methods of treatment in an adult population. Scores range from 0 (worse disability) to 100 (less disability).

To calculate the overall score, score each answer according to table 8.1.1, then sum up those scores to obtain the total score. Do not allow score to be greater than 100. If a question was left unanswered then the total score cannot be calculated..

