### 8.1.1 HHS Scoring

Domain	Item	MHHS Question	Response Scoring
Hip evaluation	1	Pain	None = 44 Slight = 40 Mild = 30 Moderate = 20 Marked = 10 Totally disabled = 0
Gait	3	Limp	None = 11 Slight = 8 Moderate = 5 Severe = 0 Unable to walk = 0
Gait	4	Distance Walked	Unlimited = 11 6 blocks (600 meters) = 8 2-3 blocks (200-300 meters) = 5 Indoors only = 2 Bed and chair = 0
Gait	5	Support	None = 11 Cane long walk = 7 Cane full time = 5 Crutch = 3 Two canes = 2 Two crutches/Walker = 0 Unable to walk = 0
Activities	7	Stairs	Normally = 4 Normally with banister = 2 Any method = 1

			Not able = 0
Activities	8	Socks/Shoes	With ease = 4 With difficulty = 2 Unable = 0
Activities	9	Sitting	Any chair, 1 hour = 5 High chair, $\frac{1}{2}$ hour = 3 Unable to sit, $\frac{1}{2}$ hour, any chair = 0
Activities	10	Public Transportation	Able to enter = 1 Unable to enter = 0
Deformity	11	Deformity	If subject did not respond then missing else If Fixed adduction $\geq$ 10 degrees or Fixed internal rotation (in extension) $\geq$ 10 degrees or Leg length discrepancy $>$ 3.2 cm or 1.25 in. or Fixed flexion $\geq$ 30 degrees Then 0 Else 4
Range of motion	12	Flexion + Abduction + Adduction + External rotation + Internal rotation	Sum all ranges then score as following: Sum $\geq$ 161 = 5 101 $\leq$ Sum $<$ 161 = 4 61 $\leq$ Sum $<$ 101 = 3

			31 <= Sum < 61 = 2
			0 <= Sum < 31 = 1
			Sum < 0 = 0

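### The 6-week Harris Hip Score depends on an optional item worth at most 5 of 100 points, so its total and change from pre-op rest on a discretionary subset of unknown size

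*Protocol*

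**What the plan says.** The Time and Events Schedule (Protocol 1.1) carries a footnote to the Harris Hip Score: "ROM optional at 6 weeks only". The 6-week visit description (Protocol 6.4) lists the assessment as "Harris Hip Score; ROM optional". Neither place says when ROM should be measured or who decides.

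Protocol 9.12.2 repeats that ROM is optional at 6 weeks and states the consequence: "the score will be missing for subjects for whom ROM was not performed". SAP 6.7.4, the matching endpoint section, does not repeat this. The scoring rule in SAP 8.1 leads to the same result, because it covers every item at every visit: "If a question was left unanswered then the total score cannot be calculated".

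The plan has no fallback. SAP 6.11 says "there will be no imputation of missing data", SAP 6.13 plans no sensitivity analyses, and neither document defines a partial, prorated or ROM-free Harris score.

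Protocol 9.6.2 lists the 6-week Harris score as a secondary endpoint, one of five post-operative time points. Change from baseline and 95% confidence intervals are planned for it.

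**The concern.** The plan makes one item optional and then lets that item decide whether the subject has a score at all. This missingness is built into the design. A subject with the other nine items answered has a total known to within 5 points, yet contributes nothing to the 6-week mean or to the change from pre-op.

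Two things are at stake. The first is precision, because the 6-week sample could be much smaller than the 30 per approach that were enrolled. The second is comparability. The 6-week mean may describe different subjects from the 3-month and later means, where ROM is not optional, and this weakens the early part of the recovery profile.

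If ROM practice differed between the two sites, the effect would also mix with surgical approach. Protocol 6.2 places the anterior approach, in general, only at the London site, and SAP 6.15 plans no formal assessment of site homogeneity.

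**Working it through.** **The plan's own figure.** The only precision figure in the documents is for 2-year subsidence (Protocol 9.8, SAP 5): 2 × 0.2 / √30 = 0.073 mm. It reproduces. There is no SD or precision target for the Harris score, so what follows is in relative terms.

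**Weight of ROM.** Item maxima from SAP 8.1.1:

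- pain 44
- limp 11, distance walked 11, support 11
- stairs 4, socks and shoes 4, sitting 5, public transportation 1
- deformity 4
- ROM 5 ("Sum all ranges then score as following", with possible values 0 to 5)

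Without ROM: 44 + 11 + 11 + 11 + 4 + 4 + 5 + 1 + 4 = 95. With ROM: 95 + 5 = 100.

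**Loss of precision.** For a given SD, the half-width of a 95% interval for a mean is proportional to t(0.975, n−1)/√n. At the planned n = 30 this is 2.045/√30 = 0.373. The share of subjects with ROM at 6 weeks is not given. The values of n below are assumptions, corresponding to ROM being skipped in roughly 25%, 50% and 75% of 30 subjects.

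| Scorable n per approach (assumed) | t/√n | Ratio to n = 30 |
|---|---|---|
| 22 | 2.080/√22 = 0.443 | 1.19 |
| 15 | 2.145/√15 = 0.554 | 1.48 |
| 8 | 2.365/√8 = 0.836 | 2.24 |

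**What the other items already tell us.** If a subject scores S on the nine other items, the full total lies between S and S + 5. If all 30 subjects have those nine items, the uncertainty in the group mean due to absent ROM is at most 5 × (30 − n)/30:

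- n = 22: 5 × 8/30 = 1.33 points
- n = 15: 5 × 15/30 = 2.50 points
- n = 8: 5 × 22/30 = 3.67 points

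**Bias.** If a fraction f is scored, and scored and unscored subjects differ by D points on average, the mean of the scored subjects is off by (1 − f) × D. With D = 5 and f = 0.5 this is 2.5 points. Both values are illustrative; the documents supply neither f nor D, nor the sign of D.

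**The case against.** The strongest reply is that this is an openly stated choice. Protocol 1.1, 6.4 and 9.12.2 agree that ROM is optional, 9.12.2 states the consequence, and SAP 8.1 is consistent with it. Declining to total an incomplete instrument is a conservative convention and fits the no-imputation rule. That stands: the documents do not contradict each other, and the point concerns an analysis choice.

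The consequences are also limited. There are no hypotheses, and the intervals are declared exploratory (Protocol 9.7, SAP 3). Function at 6 weeks is also captured by HOOS Jr., FJS-12 and the Hip Evaluation, none of which depends on ROM. The loss will be visible, because SAP 6.2 tabulates scorable Harris data separately from data on file. All of this stands, but a visible loss is still a loss. SAP 6.2 also counts a subject towards its complete-data follow-up rate only if every listed endpoint is scorable, so skipping an optional item lowers that 6-week rate too. Nor does the SAP treat incomplete instruments uniformly: SAP 8.3 scores the FJS-12 with up to 4 of 12 responses missing.

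A reader might infer three stronger things that the documents do not support:

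- **That 95 collected points are thrown away.** Ninety-five is the maximum on the other items, not what each subject scored. The responses stay in the database; only the total and its change are not computed. Some items may even be reported elsewhere: SAP 6.7.7 summarises Hip Evaluation questions at 6 weeks, and SAP 8.1.1 files pain under a domain of that name, though the overlap cannot be confirmed.
- **That the scored sample is self-selected or biased.** No selection mechanism is described, by subject, examiner or site. The subset is discretionary; bias is possible but not shown.
- **That a 0 to 95 score should become the main 6-week result.** That would replace the endpoint defined on a 0 to 100 scale and put the main 6-week result on a different scale from later visits.

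**Conclusion.** The concern holds as a weakness in a stated rule, confined to the 6-week total Harris score and quantities built on it: the change from pre-op, any correlation using it, and the 6-week complete-data rate. The primary RSA endpoint and the Harris scores from 3 months to 2 years are not touched by the optional-ROM rule.

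That ROM carries at most 5 of 100 points follows directly from SAP 8.1.1. The 1.19, 1.48 and 2.24 ratios rest on assumed scorable numbers of 22, 15 and 8 per approach, and on the SD being the same in the scored subset. If ROM is measured in nearly everyone, the loss is small. No statement about the size or direction of bias can be made from the documents.

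This is a cheap improvement: data already being collected can give a 6-week result in all subjects with the other nine items, and a like-for-like change from pre-op.

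**What to change.** Keep the 100-point Harris score and its missing-item rule as they are. Add to SAP 6.7.4 and 8.1, and align Protocol 9.12.2:

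1. A supplementary ROM-free subtotal: the sum of all items except ROM, range 0 to 95, not computed if any of those nine items is unanswered. Summarise it by approach and overall at pre-op and every later visit, with change from pre-op on the same 0 to 95 scale and 95% confidence intervals.
2. The number of subjects with ROM done and not done at 6 weeks, by approach and by site.

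The subtotal recovers the 6-week subjects who lack only ROM. The counts let a reader judge how far the 100-point result at 6 weeks comes from a particular site or approach.

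The cost is one derived variable, one extra table and a matching sentence in the protocol; no new data are collected. The downside is a second, non-standard Harris scale, which must be labelled clearly so that it is not read as the 100-point score.
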